### **8.4. Adverse Events, Serious Adverse Events, and Other Safety Reporting**

The definitions of an AE and an SAE can be found in [Appendix 3](#).

AEs may arise from symptoms or other complaints reported to the investigator by the participant (or, when appropriate, by a caregiver, surrogate, or the participant's legally

authorized representative), or they may arise from clinical findings of the investigator or other healthcare providers (clinical signs, test results, etc).

The investigator and any qualified designees are responsible for detecting, documenting, and recording events that meet the definition of an AE or SAE and remain responsible to pursue and obtain adequate information both to determine the outcome and to assess whether the event meets the criteria for classification as an SAE or caused the participant to discontinue the study intervention (see Section 7.1).

During the active collection period as described in Section 8.4.1, each participant/legally authorized representative will be questioned about the occurrence of AEs in a nonleading manner.

In addition, the investigator may be requested by Pfizer Safety to obtain specific follow-up information in an expedited fashion.

#### **8.4.1. Time Period and Frequency for Collecting AE and SAE Information**

The time period for actively eliciting and collecting AEs and SAEs (“active collection period”) for each participant begins from the time the participant provides informed consent, which is obtained before undergoing any study-related procedure and/or receiving study intervention, through and including a minimum of 28 calendar days, except as indicated below, after the last administration of the study intervention.

Follow-up by the investigator continues throughout the active collection period and until the AE or SAE or its sequelae resolve or stabilize at a level acceptable to the investigator.

When a clinically important AE remains ongoing at the end of the active collection period, follow-up by the investigator continues until the AE or SAE or its sequelae resolve or stabilize at a level acceptable to the investigator and Pfizer concurs with that assessment.

For participants who are screen failures, the active collection period ends when screen failure status is determined.

If the participant withdraws from the study and also withdraws consent for the collection of future information, the active collection period ends when consent is withdrawn.

If a participant permanently discontinues or temporarily discontinues study intervention because of an AE or SAE, the AE or SAE must be recorded on the CRF and the SAE reported using the PSSA.

Investigators are not obligated to actively seek information on AEs or SAEs after the participant has concluded study participation. However, if the investigator learns of any SAE, including a death, at any time after a participant has completed the study, and they consider the event to be reasonably related to the study intervention, the investigator must promptly report the SAE to Pfizer using the PSSA.

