## 1.2. Schema

### 1.3. Schedule of Activities

The SoA table provides an overview of the protocol visits and procedures. Refer to the **STUDY ASSESSMENTS AND PROCEDURES** section of the protocol for detailed information on each procedure and assessment required for compliance with the protocol.

The investigator may schedule visits (unplanned visits) in addition to those listed in the SoA table, in order to conduct evaluations or assessments required to protect the well-being of the participant.

Visit Identifier	Screening	Baseline (Day 1)	Day 5	Day 10	Day 14	Day 21	Day 34	ET	Notes
Visit Window	Day -1 to Day 1	0 days	0 days	±1 day	±2 days	±2 days	±3 days		
Type of Visit	In-Person Site or Home Health Visit with Telehealth	In-Person Site Visit	In-Person Site or Home Health Visit	Telehealth Visit	In-Person Site, Home Health or Telehealth Visit	Telehealth Visit	In-Person Site, Home Health or Telehealth Visit	In-Person Site, Home Health or Telehealth Visit	
ELIGIBILITY									
Informed consent	X								
 
See Section 10.1.3.
 

Verify inclusion/exclusion criteria	X								
 
See Sections 5.1 and 5.2.
 

Demographics and medical history	X								
 
COVID-19 vaccination status will be collected as part of the medical history.
 

PHYSICAL EXAMINATION & VITAL SIGNS									
Targeted physical examination	X	X	X		[X]		[X]	[X]	
 
Will be completed at all in-person visits. If not done at Screening, the procedures listed may be completed on Day 1 to assess eligibility prior to randomization and dispensing treatment.
 
Previously identified AEs (either by interview, physical exam, or other assessment) should be monitored to the extent possible if telehealth is used.
 
Targeted physical examinations see Section 8.3.1.
 
Vital signs see Section 8.3.3. (Further details for HD treatment days).
 

Vital signs	X	X	X						

Visit Identifier	Screening	Baseline (Day 1)	Day 5	Day 10	Day 14	Day 21	Day 34	ET	Notes
Visit Window	Day -1 to Day 1	0 days	0 days	±1 day	±2 days	±2 days	±3 days		

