Type of Visit	In-Person Site or Home Health Visit with Telehealth	In-Person Site Visit	In-Person Site or Home Health Visit	Telehealth Visit	In-Person Site, Home Health or Telehealth Visit	Telehealth Visit	In-Person Site, Home Health or Telehealth Visit	In-Person Site, Home Health or Telehealth Visit	
Weight, height	X		X						
 
Height may be self-reported.
 
HD treatment days will require database entry of pre- and post-dialysis weight. See Section 8.3.2.
 

LABORATORY									
Hematology	[X]	X	X		[X]		[X]	[X]	
 
Screening visit: Laboratory assessments are not required at screening unless deemed necessary by the investigator to confirm eligibility. The medical laboratory test abnormalities within 3 months prior to screening must be closely assessed.
 
Screening visit: If Laboratory assessments cannot be verified within 3 months of screening, local laboratory testing should be performed at screening to confirm eligibility for the study.
 
Baseline laboratory assessments should be collected prior to first dose of study intervention.
 
SARS-CoV-2 serology sample should be collected if an in-person (in clinic or home health) visit is conducted at Day 14±2, Day 34±3 or ET visits.
 
Safety laboratory tests (hematology, blood chemistry) at Days 14±2 and 34±3/ET are required only if clinically significant abnormal laboratory values were present from a sample drawn at the previous study visit when laboratory assessments were performed.
 
Abnormal laboratory values related to AEs should be followed until resolution. See Section 8.3.4 and Appendix 2.
 

Blood chemistry	[X]	X	X		[X]		[X]	[X]	
SARS-CoV-2 Serology (IgG and IgM)	[X]	X	X		[X]		[X]	[X]	

PFIZER CONFIDENTIAL

Visit Identifier	Screening	Baseline (Day 1)	Day 5	Day 10	Day 14	Day 21	Day 34	ET	Notes
Visit Window	Day -1 to Day 1	0 days	0 days	±1 day	±2 days	±2 days	±3 days		
Type of Visit	In-Person Site or Home Health Visit with Telehealth	In-Person Site Visit	In-Person Site or Home Health Visit	Telehealth Visit	In-Person Site, Home Health or Telehealth Visit	Telehealth Visit	In-Person Site, Home Health or Telehealth Visit	In-Person Site, Home Health or Telehealth Visit	

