Study intervention accountability			X		[X]			[X]	
 
Study intervention accountability should be performed at Day 5 visit. If Day 5 visit is prior to last dose of study intervention on Day 5, study intervention accountability can be performed at the next in-person visit (Day 14).
 
See Section 6.2.
 

Contraception check	X	X	X	X	X	X	X	X	
 
See Section 5.3.1.
 

Prior/concomitant medications	X	X	X	X	X	X	X	X	
 
All prescription and over-the-counter medications including vaccines taken by the participant within 30 days before study entry (considered prior treatment) will be recorded.
 
Concomitant therapies will be collected through the Day 34 visit.
 
See Section 6.9.
 

PFIZER CONFIDENTIAL

Visit Identifier	Screening	Baseline (Day 1)	Day 5	Day 10	Day 14	Day 21	Day 34	ET	Notes
Visit Window	Day -1 to Day 1	0 days	0 days	±1 day	±2 days	±2 days	±3 days		
Type of Visit	In-Person Site or Home Health Visit with Telehealth	In-Person Site Visit	In-Person Site or Home Health Visit	Telehealth Visit	In-Person Site, Home Health or Telehealth Visit	Telehealth Visit	In-Person Site, Home Health or Telehealth Visit	In-Person Site, Home Health or Telehealth Visit	
Adjunctive therapeutic procedures	X	X	X	X	X	X	X	X	
 
Non-drug treatments and procedures will be collected through the Day 34 visit.
 

Serious and nonserious AE monitoring	X	X	X	X	X	X	X	X	
 
AEs should be assessed by means of a telehealth visit if not feasible via an in-person visit. See Section 8.1.3.
 
See Section 8.4.
 

- Screening: Assessments indicated in brackets [X] will be performed only if needed to confirm eligibility.
- Day 1- Day 34: Assessments indicated in brackets [X] will be performed for in-person (in-clinic or home health) visits and if required per the SoA.
- Day 10 and Day 21** visits will be conducted by telehealth. Telehealth visits may be an in-person visit at the discretion of the investigator.
- Day 34 visit may be conducted by telehealth if no in-person procedures need to be performed.
- ET visit may be conducted by telehealth if no in-person procedures need to be performed or if a participant no longer wants to complete an in-person visit.

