- All efforts should be made to collect the PK sample on the day of study as designated in the PK schema for participants not on HD and for participants on HD. The visit windows listed in the SoA do not apply to the PK sample collection timepoints. Visit windows are applicable for study procedures (except PK sample collection).

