### **6.1.1. Administration**

Participants in both Cohort 1 and Cohort 2 will be given clear dosing instructions to take a single dose of PF-07321332 (nirmatrelvir)/ritonavir 300 mg/100 mg on Day 1 and PF-07321332 (nirmatrelvir)/ritonavir 150 mg/100 mg QD on Days 2 to 5.

Participants should take the first dose of study intervention on Day 1, during the in-clinic visit; that is, participants should take 2 tablets of PF-07321332 150 mg and 1 capsule of ritonavir 100 mg at the same time. Patients on HD (Cohort 2) should take their daily dose after HD.

On study Day 2, the participant selects a once daily dosing time (Day 2 dose should be taken no earlier than 14 hours and no later than 28 hours after the Day 1 dose). The doses on Days 3-5 should be taken at approximately at the same time ( $\pm 4$  hours) as the Day 2 dose. For participants on HD (Cohort 2), if Day 1 dose is taken on a non-HD day, participants should take the Day 1 dose of study intervention during the in-clinic visit; if Day 1 dose is taken on an HD day, participants should take the Day 1 dose of study intervention in the clinic after HD. On HD days, Cohort 2 participants should take their study intervention after HD.

Participants may take the study intervention with or without food. PF-07321332 (nirmatrelvir) and ritonavir should be taken than approximately 10 minutes or less apart, if feasible, but no more than 15 minutes apart. Refer to the IP manual for additional dosing and administration instructions.

If the participant misses a dose of PF-07321332 (nirmatrelvir)/ritonavir within 12 hours of the time it is usually taken, the participant should take it as soon as possible and resume the normal dosing schedule. If the participant misses a dose by more than 12 hours, the participant should not take the missed dose and instead take the next dose at the regularly scheduled time. The participant should not double the dose to make up for a missed dose.

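### The Day 34 ±3 window allows the last scheduled AE/SAE contact 1 or 2 days before the 28-day collection minimum ends after a Day 5 last dose

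*Protocol*

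**What the plan says.** **Collection period.** Protocol 8.4.1 starts active collection at informed consent and runs it "through and including a minimum of 28 calendar days, except as indicated below, after the last administration of the study intervention". The exceptions it then gives are screen failure and withdrawal of consent. An early final visit is not among them. Section 8.4 says that during this period "each participant/legally authorized representative will be questioned about the occurrence of AEs in a nonleading manner".

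**Schedule.** In the SoA, the row "Serious and nonserious AE monitoring" is marked at Screening, Days 1, 5, 10, 14, 21 and 34, and early termination. The header gives Day 34 a ±3-day window, and the laboratory notes repeat it ("visit is conducted at Day 14±2, Day 34±3 or ET visits"). A footnote applies the visit windows to every procedure except PK sampling, so AE monitoring is covered. The notes to the AE row refer to Section 8.4. Nothing is scheduled after the Day 34 visit.

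**Dosing day.** The fifth and last dose is planned for Day 5. Under 6.1.1, the "Day 2 dose should be taken no earlier than 14 hours and no later than 28 hours after the Day 1 dose", and that dose sets the usual time for Days 3 to 5. A participant who misses a dose "within 12 hours of the time it is usually taken, the participant should take it as soon as possible".

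**Endpoint.** The incidences of TEAEs, and of SAEs and AEs leading to discontinuation, are the primary endpoints (Protocol section 3). They are summarised through Day 34 (Protocol 9.3.2).

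**The concern.** The minimum in 8.4.1 counts from the last dose. The SoA window counts from a nominal study day, and nothing in the SoA ties the two together. The early part of the window opens before the 28 days have run.

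A site that schedules from the SoA table alone could hold the final contact on Day 31 or 32 and be within its window. The last day or two of the required period would then pass without active questioning. 8.4.1 also releases investigators from actively seeking events once participation has concluded, and a site might take the final visit to be that point. An event on the uncovered days would reach the database only if the participant reported it unprompted. Because SAP Appendix 2.1 reports by nominal visit using the protocol windows, a Day 31 contact would be labelled Day 34, and a tabulation by visit would not show the gap.

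What is at stake is completeness of the primary safety endpoints over the period that the protocol itself sets.

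**Working it through.** **Does the protocol itself apply the ±3 days to the last visit?** The synopsis gives a total duration of up to 38 days. Counting Day -1 plus Days 1 to 34 + 3 = 37, with no Day 0, gives 1 + 37 = 38. Stopping at Day 34 gives only 1 + 34 = 35. The stated figure is reproduced only with the full upper window, so the window does apply to the last visit.

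**Inputs**
- Minimum collection: 28 calendar days after the last dose (8.4.1).
- Final visit: Day 34 - 3 = Day 31 to Day 34 + 3 = Day 37, which is 7 permitted days (SoA).
- Planned last dose: Day 5 (SoA; 6.1.1).

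**Formula.** The day after the dose counts as day 1. Shortfall = max(0, last-dose day + 28 - visit day).

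| Calendar day of last dose | Minimum ends | Visit Day 31 | Day 32 | Day 33 | Days 34–37 |
|---|---|---|---|---|---|
| 3 | 3 + 28 = Day 31 | 0 | 0 | 0 | 0 |
| 4 | 4 + 28 = Day 32 | 1 short | 0 | 0 | 0 |
| 5 | 5 + 28 = Day 33 | 2 short | 1 short | 0 | 0 |
| 6 | 6 + 28 = Day 34 | 3 short | 2 short | 1 short | 0 |

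A last dose before Day 3 also gives no shortfall. Nominal Day 34 is 30, 29 and 28 days after a Day 4, 5 and 6 dose, so it always meets the minimum.

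**Size against the minimum.** The largest shortfall after a Day 5 dose is 2/28 = 7%, and it arises on 2 of the 7 permitted visit days. For Day 4 it is 1/28 = 4% on 1 of 7 days, and for Day 6 it is 3/28 = 11% on 3 of 7 days. These shares count permitted days. They are not probabilities.

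**Can the last dose fall on Day 6?** Yes, but only if the Day 5 dose is taken after midnight. For example, a Day 1 dose at 10:00 allows a Day 2 dose up to 28 h later, at 14:00. With 14:00 as the usual time, a Day 5 dose taken 12 h late falls at 02:00 on Day 6. A usual time after 20:00 combined with the ±4 h dosing window also passes midnight. Over all Day 1 clock times, the 14 to 28 h interval and delays up to 12 h, Day 6 is the latest day reached. Three days is therefore the maximum shortfall for a participant who takes all five doses.

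**Sensitivity to the counting rule.** If the dosing day itself counted as day 1, each shortfall would drop by one day: at most 1 day after a Day 5 dose, 2 days after a Day 6 dose, and none after a Day 4 dose. The gap would be smaller but would remain.

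**The case against.** The strongest reply is that the binding rule is already there. The 28 days are a minimum and the window is only a permission. Because 8.4.1 makes no exception for an early visit, an early visit does not shorten the period, and the duties to question, record and report follow the period rather than the visit date. The SoA introduction sends sites to the assessments section, and the AE row points to Section 8.4. Section 4.4 requires all periods of the study to be completed, and the synopsis runs safety follow-up through Day 34. A further contact is possible: "The investigator may schedule visits (unplanned visits) in addition to those listed in the SoA table".

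Most of this stands. A reader might infer that the SoA and 8.4.1 contradict each other, or that a Day 31 visit lawfully ends collection. The documents support neither inference, because a site can satisfy both rules by visiting later or adding a contact. What remains is that meeting the minimum depends on the site noticing the cross-reference and working out the date. The text on unplanned visits leaves them to the investigator and ties them to participant well-being, so it does not supply the missing contact by rule.

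A second reply is that the 3-day figure needs two uncommon things together, a Day 5 dose after midnight and a visit on the earliest permitted day. That is correct. The ordinary maximum is 2 days.

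A third reply is that safeguards remain. Telehealth visits include a reminder to report any change in health (8.1.3), spontaneously reported events are recorded (8.4.1.2), and SAEs judged reasonably related must be reported even if learned of after completion (8.4.1). These reduce the possible loss but do not replace active questioning on the uncovered days.

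**Conclusion.** The point holds as a low-severity gap in the guarantee. The permitted window allows the last scheduled AE/SAE contact 2 or 1 days before the 28-day minimum ends after a Day 5 last dose, and 1 day before it after a Day 4 last dose. The shortfall is at most 3 days, in the unusual after-midnight case. This assumes the usual count from the day after the dose, and a site that adds no further contact.

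A reader might go further and infer that the primary safety results would be biased or that events will be missed. The documents do not support that. The uncovered days come at the very end of a 28-day tail, contacts at Days 5, 10, 14 and 21 precede them, and all analyses are descriptive (Protocol 9.1). For scale only, one participant is 1/24 = 4% of the planned total and 1/12 = 8% of a cohort. How many visits would fall early, and whether any event would go unelicited, cannot be estimated from the documents. The expected effect on TEAE and SAE incidence is small.

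**What to change.** State in the Day 34 column or the AE row of the SoA that the final AE/SAE contact must be no earlier than 28 calendar days after the participant's actual last dose. Where the visit is held earlier, require a telehealth AE check on or after that day. Keep the Day 34 visit and its Day 37 upper limit.

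The cost is one sentence, or one call for a participant seen early. The Day 34 visit may already be done by telehealth when no in-person procedure is needed, and dose times are already recorded in the eDiary (8.5.5). The 38-day maximum is unchanged. The downside is slightly less scheduling flexibility: without an extra call, 5 of the 7 window days (Days 33 to 37) remain after a Day 5 dose, and 4 of 7 (Days 34 to 37) after a Day 6 dose. The change secures the 28-day minimum. It does not by itself carry every final contact to Day 34, because Day 33 would still be allowed after a Day 5 dose.

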#### **8.4.1.1. Reporting SAEs to Pfizer Safety**

All SAEs occurring in a participant during the active collection period as described in Section 8.4.1 are reported to Pfizer Safety using the PSSA immediately upon awareness and under no circumstance should this exceed 24 hours, as indicated in [Appendix 3](#). The investigator will submit any updated SAE data to the sponsor within 24 hours of its being available.

#### **8.4.1.2. Recording Nonserious AEs and SAEs on the CRF**

All nonserious AEs and SAEs occurring in a participant during the active collection period, which begins after obtaining informed consent as described in Section 8.4.1, will be recorded on the AE section of the CRF.

The investigator is to record on the CRF all directly observed and all spontaneously reported AEs and SAEs reported by the participant.

As part of ongoing safety reviews conducted by the sponsor, any nonserious AE that is determined by the sponsor to be serious will be reported by the sponsor as an SAE. To assist in the determination of case seriousness, further information may be requested from the investigator to provide clarity and understanding of the event in the context of the clinical study.

Reporting of AEs and SAEs for participants who fail screening are subject to the CRF requirements as described in Section 5.4.

#### **8.4.2. Method of Detecting AEs and SAEs**

The method of recording, evaluating, and assessing causality of AEs and SAEs and the procedures for completing and transmitting SAE reports are provided in [Appendix 3](#).

Care will be taken not to introduce bias when detecting AEs and/or SAEs. Open-ended and nonleading verbal questioning of the participant is the preferred method to inquire about AE occurrences.

#### **8.4.3. Follow-Up of AEs and SAEs**

After the initial AE or SAE report, the investigator is required to proactively follow each participant at subsequent visits/contacts. For each event, the investigator must pursue and obtain adequate information until resolution, stabilization, the event is otherwise explained, or the participant is lost to follow-up (as defined in Section 7.3).

In general, follow-up information will include a description of the event in sufficient detail to allow for a complete medical assessment of the case and independent determination of possible causality. Any information relevant to the event, such as concomitant medications and illnesses, must be provided. In the case of a participant death, a summary of available autopsy findings must be submitted as soon as possible to Pfizer Safety.

Further information on follow-up procedures is provided in [Appendix 3](#).

#### **8.4.4. Regulatory Reporting Requirements for SAEs**

Prompt notification by the investigator to the sponsor of an SAE is essential so that legal obligations and ethical responsibilities toward the safety of participants and the safety of a study intervention under clinical investigation are met.

The sponsor has a legal responsibility to notify both the local regulatory authority and other regulatory agencies about the safety of a study intervention under clinical investigation. The sponsor will comply with country-specific regulatory requirements relating to safety reporting to the regulatory authority, IRBs/ECs, and investigators.

Investigator safety reports must be prepared for SUSARs according to local regulatory requirements and sponsor policy and forwarded to investigators as necessary.

An investigator who receives SUSARs or other specific safety information (eg, summary or listing of SAEs) from the sponsor will review and then file it along with the SRSD(s) for the study and will notify the IRB/EC, if appropriate according to local requirements.

